### **10.7.2 Auditing Procedure**

In addition to the routine monitoring procedures, the Sponsor or the regulatory authority can conduct an audit or an inspection (during the study or after its completion) to evaluate compliance with the protocol and the principles of Good Clinical Practice.

The investigator agrees that representatives of the Sponsor and Regulatory Authorities will have direct access, both during and after the course of this study, to audit and review all study-relevant medical records.

### **10.7.3 Retention of Documents**

The investigator must maintain source documents for each patient in the study, consisting of all demographic and medical information, including laboratory data, and keep a copy of the signed informed consent form. All information on case report forms must be traceable to these source documents in the patient's file. Data without a written or electronic record will be defined before trial start and will be recorded directly on the case report forms, which will be documented as being the source data.

## **10.8 Disclosure of Information**

All information provided to the investigator by Ampio Pharmaceuticals, Inc. or their designee, will be kept strictly confidential. No disclosure shall be made except in accordance with a right of publication granted to the investigator.

No information about this study or its progress will be provided to anyone not involved in the study other than to Ampio Pharmaceuticals, Inc or its authorized representatives, or in confidence to the IRB, or similar committee, except if required by law.

## **10.9 Discontinuation of the Study**

Ampio Pharmaceuticals, Inc., may terminate the study at any time upon immediate notice from the Sponsor to all investigators for any reason, including the Sponsor's belief that discontinuation of the study is necessary for the safety of patients.

## **10.10 Study Report, Publication Policy and Archiving of Study Documentation**

### **10.10.1 Study Report and Publication Policy**

Depending on the outcome of the study, an ICH-compliant integrated clinical and statistical report may be prepared upon completion of the study and data analysis. The results of the study may also be published in a relevant peer-reviewed journal, with authorship status and ranking designated according to the acknowledged contributions of participating investigators, institutions and the Sponsor.

### **10.10.2 Study Documents**

The investigator must maintain source documents for each patient in the study, consisting of all demographic and medical information, questionnaires, including laboratory data, etc., and keep a copy of the signed informed consent form. All information on the e-case report forms must be traceable to these source documents in the patient's file. Data without a written or electronic record will be defined before trial start and will be recorded directly on the e-case report forms, which will be documented as being the source data.

### **10.10.3 Archiving of Documents**

Essential documents, as listed below, must be retained by the investigator for as long as needed to comply with national and international regulations. The Sponsor will notify the investigator(s)/institution(s) when the study-related records are no longer required. The investigator agrees to adhere to the document retention procedures by signing the protocol. Essential documents include:

- IRB/IEC/REB approvals for the study protocol and all amendments
- All source documents and laboratory records
- CRF copies (electronic copies on a CDROM)
- Patients' informed consent forms (with study number and title of trial)
- FDA form 1572
- Any other pertinent study document.

1. INTRODUCTION

This statistical analysis plan (SAP) outlines the proposed statistical methods to be implemented during the review of data to ensure that it confirms with categories determined by the CRF or the anticipated ranges for continuous variables and analysis of data collected within the scope of Clinical Protocol AP-019, “A Randomized, Double-Blinded, Placebo-Controlled Phase II Study to Evaluate the Safety and Efficacy of Inhaled Ampion in Adults with Respiratory Distress due to COVID-19.”

It is not intended that each and every table, listing, or graph will be included in the clinical study report (CSR). It is also possible that additional analyses will be conducted after review of the data. Any analyses or summaries not specified in the SAP, but performed after review of the data, will be identified in the CSR as post hoc.

2. OBJECTIVES

2.1 Primary

The primary trial objective is to evaluate the effect of Ampion on clinical improvement in adult participants with respiratory distress due to COVID-19.

2.2 Secondary

The secondary trial objectives evaluate the safety and efficacy of inhaled Ampion versus control in improving the clinical course and outcomes of participants with respiratory distress due to COVID-19.

2.3 Study Design

This is a Phase II randomized, double-blinded, placebo-controlled study to evaluate the safety and efficacy of inhaled Ampion in adults with respiratory distress due to COVID-19.

Interested COVID-19 patients will sign the appropriate informed consent document(s) prior to completion of any procedures. The investigator will review inclusion and exclusion criteria prior to any invasive procedures. If the patient is eligible after this review, the site will perform the necessary, if any, study procedures to confirm eligibility.

Participants will be randomized 1:1 to active or placebo using a random allocation sequence stratified by disease severity (severe, critical). The general sequence of events during the treatment and assessment period:

- Complete baseline procedures and sample collection.
- Participants are randomized to Ampion or placebo.
- Participants receive study intervention (active or placebo) inhaled via nebulization for 5 days.
- Complete safety monitoring, study procedures, and sample collection through Day 60.

All subjects will receive the standard of care (SOC) for COVID-19, which may include:

- Oxygen administration to maintain oxygen saturation of 90% or greater, including the use of supplemental oxygen, NIV, and mechanical ventilation circuits.
- Nursing physical that may include review of neurological; pulmonary; cardiac; gastrointestinal; and urinary assessment at least daily during treatment.
- Vital monitoring (heart rate, blood pressure, temperature, respiratory rate, SpO2) at least daily during treatment.
- Telemetry monitoring to evaluate heart rhythm and rate.
- Diet as tolerated to satisfy nutritional needs.
- Treatments for COVID-19 symptoms including antibiotics, cough suppressants/expectorants, anti-coagulants, fever reducers/pain killers, anti-nausea drugs, and/or bronchodilators.
- Treatments for COVID-19 as approved by the FDA including expanded access, emergency, or compassionate use (i.e., remdesivir, dexamethasone, convalescent plasma).
- Medications will be recorded as concomitant medication, tabulated, and compared among groups.

The clinical effects, safety, and tolerability of treatment will be evaluated from baseline through Day 60. Evaluations at screening and during the 5-day treatment occur in person. Evaluations after the 5- day treatment to the end of the study (days 7 to 60) will typically occur via telephone contact unless the patient is in an inpatient setting.

2.4 Sample Size

The trial is designed for approximately 200 patients across two treatment arms (active or control), with a 100 subjects per arm, randomized 1:1 using a random allocation sequence stratified by COVID-19 disease severity (severe or critical).

The number of participants is selected based on the effects observed for the primary endpoint, all-cause mortality. A study in the New England Journal of Medicine with over 4,000 patients receiving the standard of care (SOC) for COVID-19 found a 26% mortality rate at Day 28 (NEJM 384;8, February 25, 2021). There was a similar observation in the Ampion Phase I study (AP-014) for patients with respiratory distress due to COVID-19 with a mortality for the SOC control arm of 21% by Day 28. In the AP-014 study, a lower mortality rate (8%) was observed for subjects receiving inhaled Ampion. Assuming the same proportions of deaths (8% for Ampion and 26% for control) by Day 28, the number of subjects (n=200) achieves at least 80% power.

3. STUDY ENDPOINTS AND COVARIATES

3.1 Primary Endpoint:

The primary endpoint assesses the effect of Ampion compared to placebo on clinical improvement. Clinical improvement is measured as the change in ordinal scale from baseline through Day 5 and Day 28.

3.2 Secondary Endpoints

Secondary endpoints assess the effect of inhaled Ampion treatment compared to placebo on the clinical outcomes for participants with respiratory distress due to COVID-19 as follows:

Objective	Endpoint
Secondary	
Assess the effect of Ampion compared to placebo on safety	
Incidence of adverse events (AEs) and serious adverse events (SAEs) from baseline to Day 60.
Assess the effect of Ampion compared to placebo on clinical health	
Change in NEWS2 score from baseline through Day 5.Change in NEWS2 score from baseline to hospital discharge.
Assess the effect of Ampion compared to placebo on hospital stay	
Hospital length of stay (LOS) from admission to discharge.
Assess the effect of Ampion compared to placebo on oxygen use	
Change in baseline in oxygen use, blood oxygen saturation, and oxygen flow rate from baseline through Day 5.
Assess the effect of Ampion compared to placebo on progression to respiratory failure	
Percentage of participants who progress to respiratory failure (i.e., need for mechanical ventilation, ECMO, non-invasive ventilation) by Day 28.
Assess the effect of Ampion compared to placebo on intensive care	
Percentage of participants who require Intensive Care Unit (ICU) admission by Day 28.ICU-free days through Day 28.ICU LOS from ICU admission to discharge.
Assess the effect of Ampion compared to placebo on all-cause mortality	
Percentage of participants with a successful outcome (life) or unsuccessful outcome (death) by Day 28.

3.3 Exploratory Endpoints

Exploratory endpoints assess the effect of inhaled Ampion treatment compared to placebo on the clinical outcomes for participants with respiratory distress due to COVID-19 as follows:

Objective	Endpoint
Exploratory	
Assess the effect of Ampion compared to placebo cytokine profile	
Modulation of cytokine levels from baseline to Day 5.

4. HYPOTHESES

The primary endpoint assesses the effect of Ampion compared to placebo on clinical improvement. Clinical improvement is measured as the change in ordinal scale from baseline through Day 5 and Day 28.

Let μ_A and μ_S represent the mean changes in the ordinal scale for the three time points for Ampion and control respectively. Then it is desired to demonstrate that the mean change for Ampion is different than the corresponding mean change for the control, respectively. Formally, this is presented as:

$$H_0: \mu_A = \mu_S \text{ versus } H_A: \mu_A \neq \mu_S$$

The difference between Ampion and Placebo with respect to the change from baseline through Day 5 and Day 28 will be tested utilizing a Wilcoxon rank-sum test via PROC NPAR1WAY. To assess any potential time trends, an exploratory repeated measures analysis of variance will be performed with terms for treatment, time, and the interaction between the two. This will be done utilizing PROC GLM with the REPEATED option.

Secondary endpoints assess the effect of inhaled Ampion treatment compared to placebo on the clinical outcomes for participants with respiratory distress due to COVID-19. The secondary endpoints will be tested in a hierarchical manner in the order presented, and thus no adjustment to the alpha level is necessary:

Objective	Endpoint
Secondary	
Assess the effect of Ampion compared to placebo on safety	
Incidence of adverse events (AEs) and serious adverse events (SAEs) from baseline to Day 60.
Assess the effect of Ampion compared to placebo on clinical health	
Change in NEWS2 score from baseline through Day 5.Change in NEWS2 score from baseline to hospital discharge.
Assess the effect of Ampion compared to placebo on hospital stay	
Hospital length of stay (LOS) from admission to discharge.
Assess the effect of Ampion compared to placebo on oxygen use	Change in baseline in oxygen use, blood oxygen saturation, and oxygen flow rate from baseline through Day 5.
Assess the effect of Ampion compared to placebo on progression to respiratory failure	Percentage of participants who progress to respiratory failure (i.e., need for mechanical ventilation, ECMO, non-invasive ventilation) by Day 28.
Assess the effect of Ampion compared to placebo on intensive care	
Percentage of participants who require Intensive Care Unit (ICU) admission by Day 28.ICU-free days through Day 28.ICU LOS from ICU admission to discharge.

Assess the effect of Ampion compared to placebo on all-cause mortality	
 Percentage of participants with a successful outcome (life) or unsuccessful outcome (death) by Day 28.
--	--

The efficacy endpoints will be evaluated to estimate the treatment effect and use descriptive statistics including mean, standard deviation, percentages, minimum/maximum, and 95% confidence intervals. All endpoints will be tabulated and presented by treatment arm, cohort (moderate and severe), and timepoint. Where appropriate, data will be tabulated and presented cumulatively across cohorts and/or timepoints.

All binary outcomes are single incident percentages and thus the differences between the treatment groups will be tested using Fisher's exact test. The length of stay endpoints are also single incident endpoints the differences between the treatment groups will be tested using two sample t-test. All the other change from baseline variables are repeated assessments and will be analyzed utilizing a repeated measures analysis of variance.

Exploratory endpoints assess the effect of inhaled Ampion treatment compared to placebo on the clinical outcomes for participants with respiratory distress due to COVID-19 as follows:

Objective	Endpoint
Exploratory	
Assess the effect of Ampion compared to placebo on cytokine profile	
 Modulation of cytokine levels from baseline to Day 5.

The efficacy endpoints will be evaluated to estimate the treatment effect and use descriptive statistics including mean, standard deviation, percentages, minimum/maximum, and 95% confidence intervals. All endpoints will be tabulated and presented by treatment arm, cohort (moderate and severe), and timepoint. Where appropriate, data will be tabulated and presented cumulatively across cohorts and/or timepoints.

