### Ordinal Scale for Clinical Improvement

The clinical status will be recorded at every visit from baseline to Day 60 using the World Health Organization (WHO) “Ordinal Scale for Clinical Improvement”. This 8-point ordinal scale was created to be responsive to the eligible patient population, intervention, and course of illness of COVID-19. The score should reflect the highest level of support the subject required on the day being recorded. The following is scores are collected:

Score	Descriptor
0	No clinical or virological evidence of infection
1	No limitation of activities
2	Limitation of activities
3	Hospitalized, no oxygen
4	Hospitalized, oxygen by mask or nasal prongs
5	Hospitalized, non-invasive ventilation or high-flow oxygen
6	Hospitalized, mechanical ventilation
7	Hospitalized, ventilation + additional organ support – pressors, RRT, ECMO
8	Death

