All binary outcomes are single incident percentages and thus the differences between the treatment groups will be tested using Fisher's exact test. The length of stay endpoints are also single incident endpoints the differences between the treatment groups will be tested using two sample t-test. All the other change from baseline variables are repeated assessments and will be analyzed utilizing a repeated measures analysis of variance.

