4.2 Clinical Health

Clinical health is measured by the change in NEWS2 from baseline to Day 5, and baseline to hospital discharge.

The hypotheses to be tested are:

$$H_0: \mu_A = \mu_S \text{ versus } H_A: \mu_A \neq \mu_S$$

Where μ_A and μ_S represent the mean change from baseline in the NEWS2 score assessment through day 5 for Ampion and Placebo after randomization. The difference between Ampion and Placebo with respect to the change from baseline at day 5, or discharge if earlier, will be tested utilizing a Wilcoxon rank-sum test via PROC NPAR1WAY. To assess any potential time trends an exploratory repeated measures analysis of variance will be performed with terms for treatment, time and the interaction between the two. This will be done utilizing PROC GLM with the REPEATED option.

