6.1.2 Intent to Treat (ITT) Analysis Set

The intent-to-treat (ITT) analysis population is defined as all randomized patients. All efficacy analyses will be performed in the ITT population. Patients will be analyzed as randomized.

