8.1 Handling of Missing and Incomplete Data

All data collected under this study protocol will be included in the assessment of patient safety. Missing or incomplete AE data will assume greatest relationship to study drug and/or severity.

Incomplete adverse event and concomitant medication dates will be imputed as described in Section 11. If imputed dates are used, then they will be identified as such in the final study report. If an AE start date is missing or partially missing and no additional information is available in order to establish whether the event started before or after the dose of study drug, the event will be considered to have started after dose. Partially missing dates where the month and year is prior to Day 0 will not be classified as post dose.

For the ordinal score effectiveness endpoint analysis of clinical outcomes at Day 5 and Day 28 a sensitivity analysis will be performed for all patients that have been discharged from the hospital, cannot be reached via telephone contact, and their death status is not known. The sensitivity analysis will be performed where missing ordinal scale status at Day 5 and Day 28 will be replaced as having died (Ordinal score 8).

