9.6 Efficacy Analyses

The efficacy of treatment on the clinical course and outcome of COVID-19 will be evaluated by comparing to placebo. Summaries will be performed by severity (severe or critical), individually, and combined.

Unless otherwise specified, continuous variables will be summarized with the number of non-missing observations, mean, standard deviation, median, minimum, maximum and 95% confidence intervals displayed. Data transformation or use of rank-based tests may be used if endpoints depart substantially from a normal distribution. Categorical data will be summarized as counts, percentages and 95% confidence intervals.

Differences between treatments will be presented using mean differences and 95% confidence intervals. Endpoints will be compared between treatment groups (Ampion or control).

Except where otherwise specified, missing data will not be estimated or carried forward in any of the descriptive analyses. No multiple comparison adjustment will be done for the secondary efficacy analyses. If the data clearly violate the distribution assumptions of the model, then transformations may be applied, or rank-based methods used.

The efficacy analyses of the endpoints are detailed in Section 3 and Section 4 above.

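### The only repeated-measures procedure the SAP names, PROC GLM with REPEATED, is complete-case; for NEWS2 it would drop early discharges and deaths, and the plan conflicts on whether such a model is exploratory

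*SAP*

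**What the plan says.** SAP section 4 tests the primary ordinal endpoint by Wilcoxon rank-sum. It then adds that "an exploratory repeated measures analysis of variance will be performed with terms for treatment, time, and the interaction between the two", followed by "This will be done utilizing PROC GLM with the REPEATED option". The same pairing of an exploratory model with PROC GLM appears in SAP 4.2 for NEWS2 and SAP 4.8 for cytokines. No other repeated-measures procedure is named anywhere.

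For the secondary endpoints, Protocol 9.4.2 says: "All the other change from baseline variables are repeated assessments and will be analyzed utilizing a repeated measures analysis of variance". SAP section 4 repeats the sentence. Neither place calls the analysis exploratory or names a procedure. The endpoint subsections of the SAP say something else. In 4.2 the NEWS2 difference "with respect to the change from baseline at day 5, or discharge if earlier, will be tested utilizing a Wilcoxon rank-sum test". In 4.4 the oxygen measures get a t-test or a Wilcoxon test at Day 5.

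On who is analysed, SAP 6.1.2 says: "All efficacy analyses will be performed in the ITT population", meaning all randomized patients. On missing data, SAP 9.6 says: "Except where otherwise specified, missing data will not be estimated or carried forward in any of the descriptive analyses". SAP 8.1 adds one sensitivity analysis. It scores a missing ordinal value at Day 5 or Day 28 as death, and only for discharged patients who cannot be reached and whose vital status is unknown.

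**The concern.** PROC GLM with REPEATED takes one record per patient and discards the record if any of the repeated responses is missing. This is standard software behaviour; the documents do not mention it. A patient discharged on Day 3 without Day 4 and Day 5 values would contribute nothing, not even the values from the days before discharge.

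The model would then describe only patients observed on every modelled day. That subset is formed after randomization and can differ by arm if treatment affects discharge or death. For the exploratory time-trend models the harm is a misleading picture. It becomes more serious if the general sentence in Protocol 9.4.2 and SAP section 4 governs. NEWS2 and oxygen stand in the ordered secondary testing sequence ahead of respiratory failure, intensive care and mortality, so a distorted result on either could decide whether the later endpoints are formally tested.

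**Working it through.** **1. Which analysis applies to which variable.**

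| Variable | General text | Endpoint-specific text in the SAP | GLM REPEATED named? |
|---|---|---|---|
| Ordinal scale (primary) | Wilcoxon, plus exploratory repeated measures (Protocol 9.4.1) | Same (section 4) | Yes, exploratory |
| NEWS2 | Repeated measures, no label, no procedure | Wilcoxon at Day 5 or earlier discharge, plus exploratory repeated measures (4.2) | Yes, exploratory |
| Oxygen measures | Repeated measures, no label, no procedure | t-test or Wilcoxon at Day 5 (4.4) | No |
| Cytokines (exploratory) | Descriptive | t-test, plus exploratory repeated measures (4.8) | Yes, exploratory |

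For NEWS2 and oxygen the second and third columns disagree on which test counts.

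**2. Where missing visits come from.** Protocol 5.1.3 ties the Day 1 to 5 procedures to the index hospitalization. Protocol 7.1 foresees discharge before Day 5. The listed telephone visits are Days 28 and 60 (Protocol 1.1). Protocol 5.2 builds NEWS2 from vital signs, oxygen requirement and SpO2 taken at study visits. After discharge there is no planned source for these before Day 5, and after death there is no value. The ordinal scale is different: "The clinical status will be recorded at every visit from baseline to Day 60", scores 0 to 2 do not require hospitalization, and death is 8.

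**3. Size.** The plan gives no retention or missing-data figure to reproduce, so the rates below are assumptions. Day 1 is baseline, which leaves k = 4 visits (Days 2 to 5). With independent missingness m per visit, the share kept is (1 − m)^k.

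- m = 1%: 0.99^4 = 0.961, 192 of 200 kept.
- m = 2%: 0.98^4 = 0.922, 184 kept.
- m = 5%: 0.95^4 = 0.815, 163 kept (about 19% dropped).
- m = 10%: 0.90^4 = 0.656, 131 kept (34% dropped).

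Suppose in addition that 20% are discharged and 3% die before Day 5. The share kept at m = 5% is 0.815 × 0.77 = 0.627, so about 37% are dropped. The two losses overlap, so adding 19% and 23% to get 42% would be wrong.

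For scale, a comparison of means with 80% power at 100 per arm has 70.7% at 80 per arm, which is close to the 163 case.

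**4. Direction.** Early discharges are likely improvers. Protocol 2.3 reports preliminary mean stays of 7 versus 11 days in the Phase I study, so discharge timing may differ by arm. Take an illustrative score with these assumptions: early discharge 30% (active) versus 20% (placebo) at a change of −2, deaths 2% in each arm at +4, and all others with mean change −0.2 in both arms.

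- All patients, active: 0.30(−2) + 0.02(4) + 0.68(−0.2) = −0.656.
- All patients, placebo: 0.20(−2) + 0.02(4) + 0.78(−0.2) = −0.476. Difference −0.18.
- Early discharges deleted, active: (0.08 − 0.136)/0.70 = −0.080.
- Early discharges deleted, placebo: (0.08 − 0.156)/0.80 = −0.095. Difference +0.015.

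Under these assumptions the deletion removes the whole effect.

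**The case against.** The strongest reply is that nothing confirmatory depends on PROC GLM. All three uses are labelled exploratory, and SAP 9.6 points to sections 3 and 4 for the efficacy methods. There NEWS2 is tested by a Wilcoxon that expressly keeps early discharges, and oxygen by a Day 5 test with no repeated-measures model. This is correct as far as it goes. It does not dispose of the point, because the sentence that makes repeated measures the secondary analysis also stands in SAP section 4 and in the Protocol, without the exploratory label. The SAP does not say which text prevails.

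A reader might infer more than the documents support:

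- *That the primary analysis is damaged.* It is a Wilcoxon test and is untouched by GLM deletion, although it still needs a value at the time point tested.
- *That GLM is the planned procedure for oxygen.* SAP 4.4 does not name it.
- *That deaths and early discharges necessarily drop out of the ordinal model.* They need not, if post-discharge scores and a score of 8 are entered at each visit. SAP 8.1 itself anticipates telephone contact for discharged patients at Day 5. No text, however, says that 8 is carried to every later visit.
- *That the SAP contradicts its own ITT definition.* The definition settles who belongs to the set and in which arm; it does not promise complete data. The shortfall is in the handling of missing data.

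It is also fair to say that a mixed model is no complete cure. It assumes missing at random, and it gives NEWS2 and oxygen no meaning after death.

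**Conclusion.** The point holds within limits. The one repeated-measures procedure the SAP names analyses complete cases, and no stated rule prevents the loss. The loss is clearest for NEWS2, where discharge or death before Day 5 leaves visits that cannot be scored. It is avoidable for the ordinal scale and not established for oxygen. As written, each explicit use is exploratory. The point gains weight because Protocol 9.4.2 and the general text of SAP section 4 leave open that repeated measures is the test that counts in the hierarchy.

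The number lost cannot be fixed from the documents. They give no missing-visit, early-discharge or Day 5 death rates, and SAP section 4 refers to three time points while naming only Day 5 and Day 28. The losses of 19% and 37%, and the direction example, are illustrations under the stated assumptions. The change should be made, but it does not put the primary result in doubt.

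**What to change.** - Replace PROC GLM REPEATED with a likelihood-based mixed model, for example PROC MIXED with unstructured covariance. Include treatment, visit, treatment-by-visit, baseline value and severity stratum, and use all randomized patients with any post-baseline value. Report the Day 5 contrast.
- List the visits in each model.
- For the ordinal scale, state that death is entered as 8 at every later visit and that post-discharge scores are obtained.
- For NEWS2 and oxygen, state how discharge and death are handled, through a defined estimand or a composite score, since the mixed model alone does not settle truncation by death.
- Reconcile Protocol 9.4.2 and the general text of SAP section 4 with SAP 4.2 and 4.4, and say which test counts in the hierarchy.

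The cost is a few more lines of SAP wording in the same software, plus reliance on missing at random.
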